7.4 Prior Anti-Cancer Therapy and Surgery

For each prior anti-cancer therapy/surgery, the frequency and percentage of subjects who had the prior anti-cancer therapy/surgery will be provided. In addition, the number of cycles and treatment duration will be summarized for prior anti-cancer therapy.

There will be no statistical comparison for prior anti-cancer treatment/surgery between treatment arms.

8.0 Subject Disposition

Subject disposition (number and percentage of subjects) will be presented on all subjects who are screened by investigator site and overall. The following information will be presented:

- Subjects who were screened
- Subjects who screen failed
- Subjects who were randomized
- Randomized subjects who were DLL3^{high}
- Subjects who were included in the Per Protocol Set
- Subjects who took at least 1 dose of blinded study drug
- Subjects who discontinued the study drug (by primary reason and by any reason)
- Subjects who discontinued the study (by primary reason and by any reason)

Primary and all reasons for study drug discontinuation will be summarized by each of rovalpituzumab tesirine and dexamethasone.

No statistical tests will be performed.

9.0 Study Drug Exposure

Analyses for rovalpituzumab tesirine exposure will be performed on the Safety Set.

Duration of rovalpituzumab tesirine treatment, defined as the total number of weeks a subject received rovalpituzumab tesirine, accounting for (1) study drug was administered on Day 1 of each 6-week cycle, and (2) every 3rd cycle was omitted:

Treatment cycle #*	Duration of Rova-T treatment (weeks)	Theoretical duration of Rova-T treatment (weeks)	Planned dose (mg/kg)
1 + 3 × X [†]	(Date of last dose – date of first dose + 42)/7	6 × (1 + 3 × X)	0.3 + 0.6 × X
2 + 3 × X	(Date of last dose – date of first dose + 84)/7	6 × 3 × (1 + X)	0.6 × (1 + X)

* The last treatment cycle that subject received non-zero dose of Rova-T.

† X = 0, 1, 2, ... corresponding to Cycle 1, 2, 4, 5....

Summary statistics for duration of rovalpituzumab tesirine treatment will be presented by treatment arm for the following categories: ≤ 6 weeks, 6 to ≤ 18 weeks, 18 to ≤ 24 weeks, 24 to ≤ 36 weeks, etc.

Cumulative dose, defined as the sum of the doses (mg/kg) administered to a subject during the treatment period, and will be summarized by N, mean, standard deviation (St. Dev.), median, minimum, and maximum. Summary statistics for average dose administered by treatment arm will be presented at each cycle.

Dose intensity (mg/kg/week), defined as the ratio of the total dose received to the total duration of exposure.

$$DI_{observed} = \frac{\text{Cumulative dose (mg/kg)}}{\text{Duration of treatment (weeks)}}$$

Relative dose intensity 1 (RDI₁) is calculated as the ratio of observed dose intensity to the theoretical dose intensity indicated in the protocol, expressed in percent (%).

$$DI_{protocol} = \frac{\text{Planned dose } \left(\frac{mg}{kg}\right)}{\text{Theoretical duration of treatment (weeks)}}$$

$$RDI_1(\%) = \frac{DI_{observed}}{DI_{protocol}} \times 100$$

Relative dose intensity 2 (RDI₂) is calculated as the ratio of cumulative dose to the planned dose indicated in the protocol, expressed in percent (%).

$$RDI_2(\%) = \frac{\text{Cumulative dose (mg/kg)}}{\text{Planned dose (mg/kg)}} \times 100$$

Summary statistics for RDI₁ and RDI₂ will be presented. The number of subjects in the following categories (e.g., RDI < 70%, 70% to < 90%, 90% to < 110%, 110% to < 120%, 120% or higher) will also be presented.

10.0 Efficacy Analysis

10.1 General Considerations

Efficacy endpoints of response and progression used in analyses per Central Radiographic Assessment Committee (CRAC) and investigator assessment will be based RECIST v1.1. For subjects whose tumor meets the criteria of complete or partial response (CR or PR), tumor response must be confirmed by repeated assessments. Disease progression will be defined as radiographic progression of disease.

The statistical comparisons for the primary and secondary endpoints will be done according to the multiplicity adjustment plan described in Section 4.7 to preserve the familywise one-sided type 1 error rate to 2.5%. The statistical comparisons for all the exploratory efficacy endpoints will be performed at a nominal one-sided 2.5% significance level. Confidence intervals for parameters (e.g., median survival times, HR) will be constructed with 2-sided 95% confidence level, whenever applicable. No type I error adjustment for multiple comparisons will be carried out for these exploratory endpoints.

10.1.1 Statistical Analysis Methods

Time-to-Event Endpoints

All time to event (TTE) endpoints are defined using a time variable and an event indicator. All TTE efficacy endpoints in this study are concerned with only the

first occurrence of the event of interest, all recurrence of the same event is not considered for endpoint derivation or analysis. An event however may be defined in a composite manner, i.e., as the occurrence of one among several different outcomes. The composite event is observed when at least one of the component events occurs, and the time to the earliest among the occurring component events is considered to be the TTE for the composite event.

The time variable will be computed in days and converted into months (1 month = 30.4375 days). Thus, for subjects who experience the event of interest, time to event will be defined as the time from randomization to the first occurrence of the event. When multiple assessments are needed to ascertain the occurrence of an event, the earliest date among all of these assessments is taken to be date of the event or censoring. For a subject who does not experience an event on the study, time will be right censored at the time of his last available adequate post-baseline assessment that rules out the occurrence of the event. If a subject had no post-baseline assessment and did not experience the event of interest, then TTE will be censored at the date of randomization and we will set TTE = 1 day, by convention.

Follow-up time for TTE endpoints will be derived as follows:

$$\text{TTE} = \text{Date of first occurrence of an event or censoring} - \text{date of randomization} + 1.$$

TTE endpoints will be summarized by number of events observed, number of subjects censored, and times corresponding to 25% (1st quartile), 50% (median) and 75% (3rd quartile) event probabilities. Kaplan-Meier (KM) estimates will be calculated and plotted. Comparison between treatment arms will be based on stratified log-rank tests as specified.

A Cox proportional-hazards regression model with the treatment group and stratification factors as covariates will be used to estimate the hazard ratio (HR) of rovalpituzumab tesirine to placebo and its two-sided 95% confidence interval (CI).^{2,3} Only the main effects of the stratification variables will be fitted.

In the presence of sparse strata that could potentially lead to biased treatment effect estimation and/or model convergence issue, the following modified stratification factors would be used:

- RECIST v1.1 response after completion of first-line platinum-based therapy at screening assessment (SD vs. PR/CR),
- DLL3 expression (Unknown or 0% to < 75% vs. 75% or above),
- History of CNS metastases (Yes vs. No),
- For subjects with no history of CNS metastases, PCI vs. no PCI.

In cases the treatment effect estimation and/or model convergence issues persist with above modified stratification factors, and RECIST v1.1 response after completion of first-line platinum-based therapy has been confirmed not prognostic of disease outcome, this factor could be removed from both stratified log-rank test and Cox proportional hazards model.

Measure of treatment effects will be provided in terms of HR (rovalpituzumab tesirine to Topotecan) from the above model with HR value less than 1 representing treatment benefit.

Continuous Variables and Changes from Baseline

Summary of continuous endpoints at baseline, post-baseline and change from baseline (as available) will be provided by treatment arms. Change from baseline values will be analyzed using an analysis of covariance (ANCOVA) model including stratification factors and baseline as covariates and 95% CI for treatment group difference will be provided. For change from baseline analysis of PROs, patients with missing baseline value will be excluded. These summaries will also be further broken down by individual levels of each stratification factors.

Categorical Variables and Response Rates in the Study

Summary of categorical endpoints (e.g., frequency, percentage) will be provided by treatment arms. The response rates in treatment arms will be compared using Cochran-Mantel-Haenszel test stratified by randomization stratification factors. Rates and 95% confidence intervals will be reported for each treatment arm.

Stratification Factors Used in Statistical Tests and Models

Since approximately 75% of subjects enrolled are expected to have DLL3 expression $\geq 75\%$, very sparse data is expected in the three remaining strata for DLL3 expression (namely, Unknown, 0% to $< 25\%$ and 25% to $< 75\%$) that can lead to loss of power for the stratified log rank test, Cochran-Mantel-Haenszel test, ANCOVA, and result in instability and biases in estimation of parameters of the Cox regression model.

Hence, all categories of DLL3 expression $< 75\%$ or unknown will be combined into one category for analysis. If a statistical estimation procedure does not converge even after simplification of the DLL3 expression-based stratification, additional variable selection methods will be employed based on univariate assessment of the prognostic importance of individual factors on the associated endpoint (using an ad hoc p-value threshold of 0.2) and consideration of pairwise correlations between factors. If statistical models, tests and estimation remain unstable after the previous step or no other factors can be dropped from analysis, an unstratified analysis will be performed.

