4.4 Sample Size

There are two primary efficacy endpoints for this study: Progression-free survival (PFS) based on the CRAC and overall survival (OS) in DLL3^{high} ED SCLC subjects. To maintain the overall 1-sided type I error rate at a 2.5% for this study, the type I error will be split, assigning 0.25% to progression-free survival and the remaining 2.25% to overall survival. However, the OS endpoint will be tested as a one-sided 2.2499% significance level as a one-sided alpha of 10^{-6} will be spent for the early look at the OS data for futility analysis.

Sample size of the study is primarily determined by the analysis of OS. It is assumed, taking into account the expected patient population for the study, that median overall survival in the placebo and rovalpituzumab tesirine arm will be around 9 months and 13 months, respectively. The increase of median OS in rovalpituzumab tesirine arm corresponds to a hazard ratio of 0.69, i.e., a reduction in the hazard of death by 31%. With all these assumptions, a total of 319 deaths among subjects with DLL3^{high} are needed to achieve 90% power based on a log-rank test at a one-sided significance level of 0.022499. Assuming a 19-month accrual period and the last enrolled subject followed for 12 months, at least 480 subjects with DLL3^{high} are expected to be randomized (240 subjects in each arm). A total of 740 subjects regardless of DLL3 expression level (including 480 subjects with DLL3^{high}) will enroll in the study, assuming an approximate prevalence of 65% for subjects with DLL3^{high}.

The primary endpoints of OS and PFS will be analyzed at the same time after observing at least 319 OS events in subjects with DLL3^{high}. It is expected that approximately 420 PFS events assessed by the CRAC will be observed at the time of the primary analysis.

It is assumed, taking into account the expected patient population for the study, that median progression-free survival for the placebo and rovalpituzumab tesirine arm will be approximately 3 months and 4.5 months, respectively. The increase of median progression-free survival in rovalpituzumab tesirine arm corresponds to a hazard ratio of 0.667. With all these assumptions, a total of approximately 420 PFS events assessed by the CRAC for the subjects with DLL3^{high} are needed to achieve 91% power based on a log-rank test at a one-sided significance level of 0.0025.

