10.2 Efficacy Endpoints and Analyses

10.2.1 Primary Efficacy Endpoints

The primary efficacy endpoints are:

- Progression-free survival (PFS) determined by the CRAC
- Overall survival (OS)

Progression Free Survival (PFS)

PFS will be defined as the number of months from randomization to disease progression, as assessed by the CRAC per RECIST v1.1, or death of any cause, whichever occurs first. Any death that occurs > 12 weeks (two consecutive missing scans) after the previous radiographic disease assessment, or any PD or death happened after the initiation of new anti-cancer therapy will be excluded disregarded from the analysis. Subject without an event will be censored at the last date of post-baseline radiographic assessment. Subject with no post-baseline assessment and did not experience death event within 12 weeks of randomization will be censored at the date of randomization.

Differences between the treatment arm and the placebo arm in PFS will be assessed by a log-rank test stratified by the randomization stratification factors, testing the null hypothesis (rovalpituzumab tesirine arm is not superior to placebo arm in PFS). The hazard ratio of the treatment arm over the placebo arm will be calculated by a Cox's proportional hazards regression model adjusting for the main-effects of the stratification factors. Median PFS and 95% confidence intervals will be estimated using Kaplan-Meier survival methodology, with the Kaplan-Meier survival curves presented to provide a visual description. PFS rates at 3, 6, 9, and 12 months after randomization with 95% confidence intervals will be reported. Estimates of the treatment effect will be expressed as hazard ratio including 95% confidence intervals estimated through a Cox proportional-hazards regression model adjusting for the main-effects of the stratification factors. The same methodology will be applied to PFS based on investigator assessment.

Overall Survival (OS)

OS is defined as time from the randomization to death due to any cause. For subjects who are alive at the end of this study, OS will be right-censored on the last date the subject is known to be alive.

Differences between the treatment arm and the placebo arm in OS will be assessed by a log-rank test stratified by the randomization stratification factors, testing the null

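### The SAP's fallback rules for the strata of the confirmatory tests conflict, have no order of precedence, and need not be applied on blinded data

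*SAP*

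**What the plan says.** SAP 10.2.1 states that arm differences in PFS and in OS "will be assessed by a log-rank test stratified by the randomization stratification factors" and goes no further. Protocol 8.1.4 specifies the same test. SAP 10.1.1 then gives two more rules.

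- **Under the time-to-event heading.** If strata are sparse enough to threaten the treatment estimate or convergence, DLL3 goes from four levels to two. If such problems persist and RECIST response has been confirmed as not prognostic, "this factor could be removed from both stratified log-rank test and Cox proportional hazards model".
- **Under the heading on stratification factors.** All DLL3 levels below 75%, and unknown, "will be combined into one category for analysis", without any condition. If an estimation procedure still does not converge, factors are selected by "univariate assessment of the prognostic importance of individual factors on the associated endpoint (using an ad hoc p-value threshold of 0.2", together with pairwise correlations. If results stay unstable, or nothing more can be dropped, the analysis becomes unstratified.

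The reason offered for pooling begins "Since approximately 75% of subjects enrolled are expected to have DLL3 expression" at or above 75%. SAP 4.4 sized the trial "assuming an approximate prevalence of 65% for subjects with" DLL3-high disease.

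**The concern.** The strata are part of the definition of the log-rank test. Two statisticians following this SAP in good faith could compute different p-values for OS or PFS and each cite a section in support.

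Nothing says which rule governs. The SAP does not define when strata count as sparse, when results count as unstable, or what confirms that response is not prognostic. It does not require any of these decisions to be made on pooled, blinded data. One trigger, a persisting problem with estimating the treatment effect, can be recognised only after fitting a model that contains treatment. Finalizing the SAP before unblinding (SAP 3.0) therefore does not settle which test will be run.

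At stake is discretion over the strata once results are visible, in a plan that otherwise accounts for alpha down to one part in a million.

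**Working it through.** **1. The plan's own figures.** Inputs from SAP 4.4: 319 deaths "are needed to achieve 90% power based on a log-rank test at a one-sided significance level of 0.022499", HR 0.69 (medians 9 and 13 months), 1:1 allocation. Schoenfeld's formula for 1:1 allocation is d = 4(z_α + z_β)² / (ln HR)².

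- OS: 4 × (2.0047 + 1.2816)² = 43.2. Dividing by (ln 0.69)² = 0.1377 gives 314. Dividing by (ln 9/13)² = 0.1352 gives 319.5. The stated 319 is reproduced.
- PFS (HR 0.667, one-sided 0.0025, 91% power): 4 × (2.807 + 1.341)² / (ln 0.667)² ≈ 420, as stated.

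The event counts are sound and do not depend on which strata rule applies.

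**2. Starting strata.** Response has 2 levels. CNS/PCI status has 3: CNS history; no CNS history with PCI; no CNS history without PCI. DLL3 has 4 levels, or 2 when pooled.

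| Set | DLL3 as randomized | DLL3 pooled |
|---|---|---|
| DLL3-high | 2 × 3 × 1 = 6 | 2 × 3 × 1 = 6 |
| Randomized | 2 × 3 × 4 = 24 | 2 × 3 × 2 = 12 |

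Everyone in the DLL3-high Set is at 75% or above (SAP 5.0), so pooling cannot alter the primary tests. The average stratum there holds 319/6 ≈ 53 deaths or 420/6 = 70 PFS events. Conditional versus unconditional pooling matters only in the Randomized Set, for H02 and H03 and for the ANCOVA covariates of H04.

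**3. Fallbacks for the primary tests, side by side.**

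| Source | Trigger | Permitted change |
|---|---|---|
| SAP 10.2.1, protocol 8.1.4 | none | none |
| SAP 10.1.1, time-to-event text | estimation or convergence problem persists, and response confirmed not prognostic | response may be removed (optional) |
| SAP 10.1.1, stratification-factor text | non-convergence after pooling | factors selected by a 0.2 screen on the same endpoint; then unstratified |

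**4. What the choice is worth.** Stratified log-rank tests were simulated for 480 DLL3-high patients with placebo median 9 months, uniform accrual over 19 months, data cut at the 319th death, blocks of four within strata, and one-sided α 0.022499. The following are assumptions, not in the documents: 75% PR/CR; 20/35/45% CNS history/PCI/no PCI; log-HR for SD versus PR/CR of 0, 0.3 or 0.6; and, in the last two settings, CNS/PCI log-HRs of +0.3, −0.3 and 0. The four candidates are all 6 strata, response dropped, CNS/PCI dropped, and unstratified. There were 20,000 null runs per setting (SE about 0.1 point) and 4,000 at HR 0.69.

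| Log-HR, response | 0 | 0.3 | 0.6 |
|---|---|---|---|
| Type I, 6 strata | 2.48% | 2.30% | 2.21% |
| Type I, 0.2 screen always applied | 2.51% | 2.29% | 2.21% |
| Type I, most favourable of four | 2.92% | 2.73% | 2.84% |
| Verdict differs among the four, null | 0.8% | 1.1% | 1.4% |
| Verdict differs among the four, HR 0.69 | 2.4% | 3.5% | 5.3% |
| Power, 6 strata | 90.4% | 90.9% | 90.1% |
| Power, unstratified | 90.3% | 89.9% | 88.0% |

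**5. DLL3-high share.** At 75%, 740 × 0.25 = 185 subjects fall outside DLL3-high. With the design's 480, 740 − 480 = 260 do (480/740 = 64.9%). Over 3 × 6 = 18 unpooled cells that averages about 10 or 14 subjects per cell.

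**The case against.** The case for leaving the text alone has real force.

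- **The primary tests start from one place.** A reader might infer that the SAP gives three different stratifications for primary OS and PFS. It does not. DLL3 is constant in that set, and only the fallbacks differ.
- **The 0.2 screen is gated.** A reader might infer that factors may be dropped whenever they miss p = 0.2. The text requires non-convergence after pooling first, and the unstratified step lies behind the same gate. A log-rank test has no iterative fit. The Cox model uses main effects only, about four parameters on 319 deaths. Failure to converge in the DLL3-high Set is unlikely.
- **The screen ignores treatment.** Applied every time, it left type I error where full stratification does.
- **No rule permits choosing strata by the treatment p-value.** The 2.7–2.9% is a worst case for misuse, not the error rate of the written procedure. H02 is also protected because it is tested only after H01b is rejected.
- **Pooling DLL3 is sensible at either share.** With 10 or 14 subjects per cell, nobody would want 24 strata.

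All of this stands, and it limits the size of the point. It does not remove it. The time-to-event rule reaches the log-rank test itself, is optional, and can be triggered by a perceived problem with the treatment estimate. The gate on the second rule does not say which rule prevails, and the Randomized Set rules contradict each other outright.

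**Conclusion.** The point holds in limited form. The SAP's rules for the strata of its confirmatory tests are not identical, have no precedence and rest on undefined triggers. For the primary tests the conflict is among fallbacks. For H02, H03 and H04 it includes the starting strata or covariates.

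The numerical exposure is modest: nothing measurable from the screen itself, and about 0.4 to 0.6 percentage points above the 6-stratum test if strata were picked on results. At the design effect, about 2–5% of trials would change verdict with the strata. These sizes rest on the assumed prognostic effects and stratum shares, and on IRT strata agreeing with the DLL3-high classification. The textual conflict rests on no assumption.

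Two stronger conclusions are not supported: that type I error is inflated as planned, and that the 75% share is the wrong figure. SAP 10.1.1 describes an expectation for enrolled subjects and SAP 4.4 a design assumption. The documents do not say whether one updates the other.

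**What to change.** Amend the SAP before unblinding so that one rule governs and 10.2.1 refers to it:

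- **DLL3-high Set:** log-rank test stratified by response (2) × CNS/PCI status (3), 6 strata.
- **Randomized Set:** the same, × DLL3 (75% or above versus below 75% or unknown), 12 strata. Use the same factors as covariates for H04.
- **Delete, for confirmatory tests:** the optional removal of response, the 0.2 screen and the unstratified fallback.
- **Separate test from estimate:** a Cox fitting problem must not change the log-rank strata. A reduced Cox model may be reported, labelled as such, with the p-value unaffected.
- **If merging is kept:** write in a numeric minimum of pooled events per stratum and a fixed order, for example PCI with no PCI first, then CNS history with the rest. Apply it to blinded pooled data and document it before unblinding.
- **Reconcile** the 75% and 65% DLL3-high shares, or say why they differ.

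The cost is SAP wording and some lost discretion if a model proves awkward to fit. The 319 deaths and 90% power are unchanged. In the simulations the 6-stratum test had 90–91% power against 88–90% unstratified.

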10.2 Efficacy Endpoints and Analyses

10.2.1 Primary Efficacy Endpoints

The primary efficacy endpoints are:

- Progression-free survival (PFS) determined by the CRAC
- Overall survival (OS)

Progression Free Survival (PFS)

PFS will be defined as the number of months from randomization to disease progression, as assessed by the CRAC per RECIST v1.1, or death of any cause, whichever occurs first. Any death that occurs > 12 weeks (two consecutive missing scans) after the previous radiographic disease assessment, or any PD or death happened after the initiation of new anti-cancer therapy will be excluded disregarded from the analysis. Subject without an event will be censored at the last date of post-baseline radiographic assessment. Subject with no post-baseline assessment and did not experience death event within 12 weeks of randomization will be censored at the date of randomization.

Differences between the treatment arm and the placebo arm in PFS will be assessed by a log-rank test stratified by the randomization stratification factors, testing the null hypothesis (rovalpituzumab tesirine arm is not superior to placebo arm in PFS). The hazard ratio of the treatment arm over the placebo arm will be calculated by a Cox's proportional hazards regression model adjusting for the main-effects of the stratification factors. Median PFS and 95% confidence intervals will be estimated using Kaplan-Meier survival methodology, with the Kaplan-Meier survival curves presented to provide a visual description. PFS rates at 3, 6, 9, and 12 months after randomization with 95% confidence intervals will be reported. Estimates of the treatment effect will be expressed as hazard ratio including 95% confidence intervals estimated through a Cox proportional-hazards regression model adjusting for the main-effects of the stratification factors. The same methodology will be applied to PFS based on investigator assessment.

Overall Survival (OS)

OS is defined as time from the randomization to death due to any cause. For subjects who are alive at the end of this study, OS will be right-censored on the last date the subject is known to be alive.

Differences between the treatment arm and the placebo arm in OS will be assessed by a log-rank test stratified by the randomization stratification factors, testing the null

hypothesis (rovalpituzumab tesirine arm is not superior to placebo arm in OS). The hazard ratios of the treatment arm over the placebo arm will be calculated by a Cox's proportional hazards regression model adjusting for the main-effects of the stratification factors. Median OS and 95% confidence intervals will be estimated using Kaplan-Meier survival methodology, with the Kaplan-Meier survival curves presented to provide a visual description. OS rate at 6, 12, 18, and 24 months and corresponding 95% confidence intervals will be reported. Estimates of the treatment effect on will be expressed as hazard ratio including 95% confidence intervals estimated through Cox proportional-hazards regression models adjusting for the main-effects of the stratification factors.

